For research relying on a non-UT Southwestern IRB (external, central, or single IRB):

Investigators relying on an external IRB who are conducting research on behalf of UT Southwestern or its affiliates are responsible for submitting LOCAL UPIRSOs to the UT Southwestern IRB within 5 working days of study team awareness. Investigators must report to their relying IRB according to the relying IRB's policy. In addition, the external IRB's responses or determinations on these local events must be submitted to the UT Southwestern IRB within 10 working days of receipt.

Events NOT meeting UPIRSO criteria:

Events that do NOT meet UPIRSO criteria should be tracked, evaluated, summarized, and submitted to the UTSW HRPP/IRB at continuing review.

For more information on UTSW HRPP/IRB reportable event policy, see https://www.utsouthwestern.edu/research/hrpp/guality-assurance/

7.4 Unblinding Procedures

7.5 Stopping Rules

N/A

8.0 DRUG/TREATMENT INFORMATION

Not applicable for this trial.

9.0 CORRELATIVES/SPECIAL STUDIES

9.1 Specimen Banking

No specimen banking will be explicitly performed for this study.

10.0 STATISTICAL CONSIDERATIONS

10.1 Study Design/Study Endpoints

- 10.1.1 Primary endpoint: 2-year risk of local failure (i.e. anywhere in the larynx) following SBRT treatment of early glottic larynx cancer
- 10.1.2 Secondary endpoints:
 - 10.1.2.1 Patient-reported outcomes: Difference in PRO measures between baseline and 1, 3, 6, 12, 18, 24 and 36 months following treatment:

10.1.2.1.1 VHI voice-quality score10.1.2.1.2 EORTC QLQ30 and HN35 scores

10.1.2.2	Rate of grade 3-5 acute (start of treatment through 90 days from the completion of treatment) and late (after 90 days from the completion of treatment) adverse events, according to NCI's CTCAE v4.0 toxicity criteria.
10.1.2.3	Average patient utilities (derived from EQ-5D) at baseline and 1, 3, 6, 12, 18, 24 and 36 months from the end of treatment
10.1.2.4	Cumulative risk of marginal and out-of field local failure at 2 years from the start of treatment with death and prior in-field local failure as a competing risk
10.1.2.5	Cumulative incidence of regional failure and distant metastasis at 2 years, with death and prior locoregional failure as competing risks
10.1.2.6	Laryngectomy-free survival probability at 2 years
10.1.2.7	Overall survival at 2 years

10.2 Sample Size and Accrual

The general perception in the radiotherapy community is that radiotherapy for early stage glottic larynx cancer leads to a local control probability of approximately 95%. Given there are some T2 patients on the study (bigger tumors), we use the 2-year local control rate of 90% rather than 95% with the non-inferiority margin of 15%. The hazard rates for 2-year local control probabilities of 90% and 75% are 0.0527 and 0.1438, respectively. With a sample size of 25 patients, this study has more than 80% power to detect a non-inferiority against an upper hazard ratio bound of 2.73 (=0.1438/0.0527) using a log-rank test at a significance level of 0.1 when the actual hazard ratio is 1.0 and the reference group hazard rate is 0.0527. Patients will be accrued for a period of 3 years with 2-year follow-up. This assumes that a local control outcome inferior to 75% would obviate the potential benefit of highly focal radiation treatment.

Our prior phase I study included a nearly identical patient population and took just over 3 years to complete; however, this protocol has 2 periods of a 90 day halt on new accrual because it was a phase I study. Therefore we expect the present proposal to be completed in 2.5 to 3 years.

10.3 Data Analyses Plans

10.3.1 Primary endpoint: 2-year cumulative risk of local failure (i.e. anywhere in the larynx) following SBRT treatment of early glottic larynx cancer

This endpoint will be calculated using cumulative incidence statistics, with death as a competing risk.

10.3.2 Secondary endpoints:

Patient-reported outcomes: Difference in PRO voice quality measures between baseline and 1, 3, 6, 12, 18, 24, and 36 months following treatment:

10.3.2.1	VHI voice-quality score
10.3.2.2	EORTC QLQ-C30
	 Global health status
	 Physical functioning scale
	Role functioning scale
	Emotional functioning scale
	Cognitive functioning scale
	 Social functioning scale
10.3.2.3	EORTC HN35
	Speech
	 Social eating
	— • • • •

Social contact

These patient reported outcomes are single numeric scores that are collected at baseline, 1, 3, 6, 12, 18, 24 and 36 months from treatment. Patients with disease recurrence will be excluded. The changes in these outcomes from baseline to these timepoints will be analyzed using generalized estimated equations (GEE).

10.3.2.4 Rate of grade 3-5 acute (start of treatment through 90 days from the completion of treatment) and late (after 90 days from the completion of treatment) adverse events, according to NCI's CTCAE v4.0 toxicity criteria.

Only adverse events assessed to be definitely, probably, or possibly related to protocol treatment will be considered. The rates of all Grade 3-5 adverse events, and death during or within 30 days of discontinuation of protocol treatment will be characterized. Predictors of high-grade acute and late toxicity will be determined using multivariable logistic regression.

10.3.2.5Average patient utilities (derived from EQ-5D) at baseline, 3, 6,
12, 18, 24 and 36 months from the end of treatment

The average patient utilities (derived from EQ-5D) at baseline, 3, 6, 12, 18, 24 and 36 months from the end of treatment will be described. Changes in patient utility will be analyzed using generalized estimated equations (GEE). These models will be used to estimate the beta coefficient for dysphonia and grade 2-3 dysphagia, to produce an estimate of the utility decrement from this toxicity.

10.3.2.6 Cumulative risk of marginal and out-of-field local failure at 2 years from the start of treatment with death and prior in-field local failure as a competing risk

These outcomes will be calculated using classic cumulative incidence statistics, and the Fine-Gray method will be used to calculate univariable predictors of recurrence.

10.3.2.7 Cumulative incidence of regional failure and distant metastasis at 2 years, with death and prior locoregional failure as competing risks

These outcomes will be calculated using classic cumulative incidence statistics, and Gray's test will be used to calculate univariable predictors of recurrence.

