PD	Progressive Disease
PET	Positron Emission Tomography
PFS	Progression Free Survival
p.o.	peros/by mouth/orally
PR	Partial Response
RC	Regional Control
RCB	Residual Cancer Burden
RECIST	Response Evaluation Criteria in Solid Tumors
RR	Regional Recurrence
SAE	Serious Adverse Event
SCCC	Simmons Comprehensive Cancer Center
SD	Stable Disease
SEER	Surveillance Epidemiology and End Results
SGOT	Serum Glutamic Oxaloacetic Transaminase
SPGT	Serum Glutamic Pyruvic Transaminase
VHI	Voice Handicap Index
VMAT	Volumetric Modulated Arc Therapy
WBC	White Blood Cells

STUDY SCHEMA

STUDY SUMMARY

Title	Phase II Trial of Stereotactic Body Radiotherapy (SBRT) for Early- stage Glottic Larynx Cancer
Short Title	A Prospective Phase II Trial of SBRT for Early Glottic Larynx Cancer
Protocol Number	122017-043
Phase	Phase 2
Methodology	Prospective Study
Study Duration	3 years to accrue plus additional 3 years of follow-up
Study Center(s)	Single center
Objectives	To determine the local control and quality-of-life outcomes of using SBRT for early-stage glottic larynx cancer
Number of Subjects	25
Diagnosis and Main Inclusion Criteria	Stage I-II glottic larynx cancer
Study Product(s), Dose, Route, Regimen	Highly focal SBRT, delivered either every other day (low-risk) or daily (moderate-risk)
Duration of administration	3 weeks
Reference therapy	N/A
Statistical Methodology	The study has 85.6% power to detect a local control probability difference of 15% (95% vs. 80%) using a two-sided, one-sample log-rank test at a 0.10 significance level.

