2.2 Secondary Objectives

2.2.1 To determine patient-reported outcomes (PRO) following treatment with SBRT.

- 2.2.2 To describe the rates of grade 3-5 acute and late toxicities following treatment with SBRT.
- 2.2.3 To characterize patient utilities using EQ5D following treatment with SABR.
- 2.2.4 To determine the patterns-of-failure following SBRT. Specifically, 2-year cumulative risk of in-field, marginal, and out-of-field local failure, regional and distant failure, laryngectomy-free survival, disease-specific survival and overall survival following treatment with SBRT.

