4.6 Duration of Follow Up

Subjects will be followed for a minimum of **3 years** after completion of treatment or until death, whichever occurs first. Specifically, subjects will be followed at 1, 3, 6, 9, 12, 18, 24, 30, and 36 months following treatment. Subjects removed from therapy for unacceptable adverse events will be followed until resolution or stabilization of the adverse event.

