4.7 Removal of Subjects from Protocol Therapy

Subjects will be removed from therapy when any of the criteria listed in Section 5.5 apply. Notify the Principal Investigator, and document the reason for study removal and the date the subject was removed in the Case Report Form. The subject should be followed-up per protocol.

Patients who are not able to complete the treatment or required follow-up procedures due to cognitive impairment will be removed from the study and treated and/or followed using standard-of-care procedures.

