5.3 Follow-up Procedures

Patients will be seen by a radiation oncologist at 1 month (+/- 1 week) and 3 months (+/- 1 week) from the completion of treatment. More frequent visits are encouraged if the patient requires additional help with recovery and rehabilitation

Patients will then be seen every 3 months (+/- 2 weeks) for the first year, and then at least every 6 months (+/-2 weeks) until the end of the 3rd year. Subsequent and intervening follow-up visits will be made per physician preference. These protocol mandated procedures will occur at each follow-up:

- Interim history
- Physical exam, vital signs, ECOG PS (vital signs are not required when patient has a Telehealth visit)
- Laryngoscopy to assess tumor response and toxicity
- Quality of life and voice quality assessment (months 1, 3, 6, 12, 18, 24 and 36)

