5.5 Removal of Subjects from Study

Subjects can be taken off the study treatment and/or study at any time at their own request, or they may be withdrawn at the discretion of the investigator for safety,

behavioral or administrative reasons. The reason(s) for discontinuation will be documented and may include:

- 5.5.1 Subject voluntarily withdraws from treatment (follow-up permitted);
- 5.5.2 Subject withdraws consent (termination of treatment and follow-up);
- 5.5.3 Subject is unable to comply with protocol requirements;
- 5.5.4 Subject demonstrates disease progression (unless continued treatment with study drug/treatment is deemed appropriate at the discretion of the investigator);
- 5.5.5 Subject experiences toxicity that makes continuation in the protocol unsafe;
- 5.5.6 Treating physician judges continuation on the study would not be in the subject's best interest;
- 5.5.7 Subject becomes pregnant (pregnancy to be reported along same timelines as a serious adverse event);
- 5.5.8 Development of second malignancy (except for basal cell carcinoma or squamous cell carcinoma of the skin) that requires treatment, which would interfere with this study;
- 5.5.9 If a research subject cannot be located to document survival after a period of 2 years, the subject may be considered "lost to follow-up." All attempts to contact the subject during the two years must be documented.

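### The VHI, QLQ-C30 and HN35 analyses exclude whole patients with recurrence and set no time limit, so as written they discard forms completed before recurrence

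*Combined protocol and SAP*

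**What the plan says.** Sections 10.3.2.1 to 10.3.2.3 list the VHI, six QLQ-C30 scales and the HN35 scales, collected at baseline and at months 1, 3, 6, 12, 18, 24 and 36. The text then says "Patients with disease recurrence will be excluded" and plans a GEE analysis of change from baseline to each visit. It does not say when the exclusion takes effect, or whether recurrence means local, regional or distant disease.

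The objectives are wider. Objective 2.2.1 reads "To determine patient-reported outcomes (PRO) following treatment with SBRT", and the Study Summary reads "To determine the local control and quality-of-life outcomes of using SBRT for early-stage glottic larynx cancer". Neither is limited to recurrence-free patients.

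Other sections bear on the point:

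- Section 4.6 sets follow-up at a minimum of three years "after completion of treatment or until death, whichever occurs first".
- Section 4.7, on patients taken off therapy, says "The subject should be followed-up per protocol".
- Section 5.3 schedules the questionnaires to month 36 and names no stop at recurrence.
- Section 5.5.4 lists "Subject demonstrates disease progression" among the possible reasons for removal from treatment and/or study.
- Section 2.4.2.1 ends the patient-reported comparisons at month 24, whereas sections 10.1.2.1 and 10.3.2 run to month 36.
- Section 10.3.2.5 plans a GEE analysis of EQ-5D utilities with no recurrence rule.

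**The concern.** Whether a patient recurs is known only after treatment, and local recurrence is the primary failure event. If a recurrence at month 30 removes the whole patient, that patient's month-1 and month-6 forms are lost too, although they were completed while the patient was disease-free. The early results then describe only patients whose disease stayed controlled later, which is narrower than objective 2.2.1.

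Two things are at stake. One is precision at the early visits, in a trial of 25 patients. The other is interpretation, because the analysed group is selected on treatment success. The method does not require the loss: GEE accepts different numbers of visits per patient, so recurrence-free voice and quality of life can be studied without deleting pre-recurrence forms.

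**Working it through.** **Inputs.** The sample size is 25 (section 10.2). Section 10.2 also gives: "The hazard rates for 2-year local control probabilities of 90% and 75% are 0.0527 and 0.1438, respectively". The post-baseline visits are months 1, 3, 6, 12, 18, 24 and 36 (section 10.3.2). The plan gives no sample size, power or variance for the patient-reported analyses, so there is no figure of its own to reproduce for them.

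**Check of the borrowed hazards.** −ln(0.90)/2 = 0.0527 and −ln(0.75)/2 = 0.1438 per year. Both agree with section 10.2. The 90% rate is the planning value and 75% is the non-inferiority limit.

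**Assumptions.** Constant hazard extended to the horizon, local failures only, no deaths, every form completed.

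**Formulas.** With 2-year control S, the probability of local failure by month m is F(m) = 1 − S^(m/24). For horizon H:

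- patients removed = 25 × F(H)
- recurrence-free forms at visit v = 25 × (1 − F(v))
- pre-recurrence forms lost at visit v = 25 × (F(H) − F(v))

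The 36-month horizon uses seven visits. The 24-month horizon uses six visits and assumes that recurrence after month 24 does not trigger exclusion.

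**Patients removed.**

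- S = 0.90: 25 × (1 − 0.90^1.5) = 3.65 by month 36; 25 × 0.10 = 2.5 by month 24.
- S = 0.75: 25 × (1 − 0.75^1.5) = 8.76 by month 36; 25 × 0.25 = 6.25 by month 24.

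**Forms per instrument** (calculated before rounding):

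| Month | Recurrence-free, 90% | Lost, H=36 | Lost, H=24 | Recurrence-free, 75% | Lost, H=36 | Lost, H=24 |
|---|---|---|---|---|---|---|
| 1 | 24.89 | 3.55 | 2.39 | 24.70 | 8.46 | 5.95 |
| 3 | 24.67 | 3.33 | 2.17 | 24.12 | 7.88 | 5.37 |
| 6 | 24.35 | 3.00 | 1.85 | 23.27 | 7.03 | 4.52 |
| 12 | 23.72 | 2.37 | 1.22 | 21.65 | 5.41 | 2.90 |
| 18 | 23.10 | 1.76 | 0.60 | 20.15 | 3.91 | 1.40 |
| 24 | 22.50 | 1.15 | 0 | 18.75 | 2.51 | 0 |
| 36 | 21.35 | 0 | – | 16.24 | 0 | – |
| Total | 164.6 | 15.2 | 8.2 | 148.9 | 35.2 | 20.1 |

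Without month 36, the recurrence-free totals are 164.6 − 21.35 = 143.2 and 148.9 − 16.24 = 132.6 (rounded).

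- 90%: 15.2/164.6 = 9% over 36 months; 8.2/143.2 = 6% over 24 months.
- 75%: 35.2/148.9 = 24% over 36 months; 20.1/132.6 = 15% over 24 months.

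**Month-6 standard error**, as the square root of the ratio of available to retained patients (equal variances, no borrowing of information across visits):

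- 90%: √(24.35/21.35) = 1.07 for 36 months; √(24.35/22.50) = 1.04 for 24 months.
- 75%: √(23.27/16.24) = 1.20 for 36 months; √(23.27/18.75) = 1.11 for 24 months.

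**Departures from the assumptions.** Regional or distant recurrences would add to the losses. Failures clustered early would reduce the number of pre-recurrence forms lost.

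**The case against.** The strongest reply is that the authors meant exclusion from recurrence onward. The sentence stands next to the visit list and can be read visit by visit. That may well be the intention, but no section states it. Two analysts could build different datasets from the same words, so the wording has to change under either reading.

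The second reply is that the loss is small. It is modest at the planned rate, and the 75% figures describe a trial at its failure limit, not its expectation. Section 1.4 reports no local failures so far in the 13 phase I patients at 42.5 Gy, and 100% 2-year control in the published 16-fraction series. Two phase I regimens not used here had 75% and 84.4%. The 75% column therefore belongs in the review only as a worst case.

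The third reply is that excluding recurrence separates treatment effects from those of salvage. That is a legitimate question, but it does not call for deleting forms completed before recurrence.

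A reader might infer more than the documents support:

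- *The rule flatters SBRT.* The plan gives no patient-reported means, variances or differences by later recurrence, so no direction or size of bias can be derived.
- *No quality-of-life analysis includes patients who recur.* The EQ-5D paragraph carries no such exclusion, although EQ-5D does not replace the voice measures.
- *Recurring patients leave the study, so nothing further could be analysed.* Section 5.5 is permissive, and sections 4.6, 4.7 and 5.3 make continued follow-up the default. Removal would in any case not justify dropping earlier forms.

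**Conclusion.** The concern holds for the rule as written. It excludes patients instead of assessments, has no time limit, discards valid pre-recurrence forms and makes early results conditional on later disease control.

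At the planned 90% control the cost is a modest loss of precision: the forms lost are 9% over 36 months or 6% over 24, and the month-6 standard error rises 7% or 4%. At the 75% limit the worst case is 8.8 patients, 24% of forms and a 20% rise over 36 months, or 6.3 patients, 15% and 11% over 24 months. These figures rest on a constant hazard, local failures only and complete forms.

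The rule should be corrected because quality of life is one of two outcomes in the summary objective and the repair is cheap. It does not threaten the primary endpoint, and no bias has been demonstrated.

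**What to change.** Replace the sentence in section 10.3.2 with: *Assessments after the date of disease recurrence will be excluded; all assessments completed before recurrence will be included.* Label the result the recurrence-free analysis, and state which recurrences (local, regional, distant) count.

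The cost is one sentence and no new visits or data. The downside is that the analysed membership changes from visit to visit, whereas whole-patient exclusion keeps a fixed cohort. If the authors do want that fixed cohort, the plan should say so and describe the results as applying only to patients who remain recurrence-free through follow-up.

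Optional additions:

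- A sensitivity GEE using all collected assessments, with the same laryngectomy cut-off for VHI and HN35 Speech. This means at least ten further models (one VHI, six QLQ-C30, three legible HN35 scales) in 25 patients, and it mixes in the effects of salvage.
- One line stating whether the EQ-5D analysis uses the same population, and one confirming that questionnaires continue after progression, so that section 5.5.4 reads consistently with sections 4.6, 4.7 and 5.3.

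### GEE on at most 25 patients has no stated small-sample correction: visit-by-visit changes are barely affected, but intervals for the utility decrement would be too narrow under the usual robust variance

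*Combined protocol and SAP*

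**What the plan says.** Section 10.3.2 covers VHI, six QLQ-C30 scales and the listed HN35 scales. On timing it says: "These patient reported outcomes are single numeric scores that are collected at baseline, 1, 3, 6, 12, 18, 24 and 36 months from treatment". That gives seven post-baseline visits. It continues: "Patients with disease recurrence will be excluded". The method is: "The changes in these outcomes from baseline to these timepoints will be analyzed using generalized estimated equations (GEE".

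Section 10.3.2.5 first describes mean utilities at baseline and six later visits, then says: "Changes in patient utility will be analyzed using generalized estimated equations (GEE". The same models are to supply a coefficient for dysphonia and for grade 2-3 dysphagia, read as the loss of utility due to each. The recurrence exclusion is written in the PRO paragraph and is not repeated for utilities.

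Section 10.2 fixes the number of patients: "With a sample size of 25 patients, this study has more than 80% power". It assumes 90% local control at 2 years.

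For the GEE analyses the plan gives no working correlation, variance estimator, small-sample correction, reference distribution or significance level. It does not say whether visits are tested one at a time or together.

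**The concern.** GEE is usually reported with the robust (sandwich) variance and a normal or chi-square reference. Both are large-sample devices, and the sample that counts is the number of patients, not the number of questionnaires. With 25 patients or fewer, the sandwich variance is biased low and the normal and chi-square cut-offs are too small.

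The effect grows in two situations. One is a coefficient identified by only a few patients, such as one for a toxicity that few people develop. The other is a test of several visits at once, where the number of parameters is no longer small relative to the number of patients.

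PROs and utilities are secondary objectives (2.2.1 and 2.2.3), and quality of life is part of the headline objective in the Study Summary. Overconfident intervals there would affect what the trial reports on voice, quality of life and the utility cost of toxicity.

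**Working it through.** The plan gives no size, standard error or power for these analyses, so there is no figure of its own to reproduce.

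**Inputs from the documents**
- Patients: n = 25 (10.2).
- PRO patients after recurrences: 25 × 0.90 = 22.5 from local failure alone, taken as 22 (10.2 and 10.3.2).
- Post-baseline visits: k = 7 for PROs (10.3.2) and k = 6 for utilities (10.3.2.5).

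**Assumptions, not in the documents**
- Uncorrected robust variance with a normal or chi-square reference.
- Two-sided 5% level.
- For the closed forms: normal, complete data and a separate mean at each visit.
- For the utility decrement: within-patient correlation 0.5 and stated numbers of affected patients.

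**1. One visit against baseline.** The robust z statistic equals a paired t statistic computed with divisor n, so the actual level is P(|t(n−1)| > 1.96 × √((n−1)/n)).
- n = 25: the standard error is short by a factor √(24/25) = 0.980. The threshold is 1.96 × 0.980 = 1.920, and the level is 6.7%.
- n = 22: the threshold is 1.96 × √(21/22) = 1.915, and the level is 6.9%.

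With strongly skewed changes the level at n = 25 is 9.2%. An ordinary paired t test gives 7.6% there, so most of that excess is not due to the robust variance.

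**2. Utility decrement.** This was simulated with 25 patients and toxicity as a patient-level indicator. Coverage of nominal 95% intervals:

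| Patients affected (of 25) | Robust variance, normal reference | Mancl-DeRouen, t reference |
|---|---|---|
| 3 | 82% | 91% |
| 4 | 86% | 93% |
| 6 | 90% | 95% |
| 10 | 92% | 96% |

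Separate runs gave 80% for 3 patients, 85-86% for 4 and 88-90% for 6, so the figures are good to about two points. If toxicity instead comes and goes by visit (15% of visits missing), the uncorrected test runs at 9.3% when 20% of visits are affected and 14.7% when 5% are.

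**3. Joint test of all visits, if one were run.** The robust Wald statistic is a Hotelling T² with divisor n referred to chi-square, so the level is P(F(k, n−k) > q × (n−k)/(k × n)). Here q is the 95% chi-square point: 14.07 for k = 7 and 12.59 for k = 6.
- PROs, n = 25: 14.07 × 18/175 = 1.447, level 24.8%.
- PROs, n = 22: 14.07 × 15/154 = 1.370, level 28.7%.
- Utilities, n = 25: 12.59 × 19/150 = 1.595, level 20.3%.

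To separate the causes, replace divisor n by n − 1 in the first case: 14.07 × 18/168 = 1.507, level 22.7%. Removing the bias in the variance therefore takes away 24.8 − 22.7 = 2.1 of the 24.8 − 5 = 19.8 excess points. The rest comes from using chi-square where F is needed.

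**The case against.** The strongest reply is that the plan mainly describes change from baseline to each visit, and there the effect is small: a 2% shortfall in the standard error at n = 25 and a level of 6.7%. That stands. A reader might infer that every PRO and utility test runs well above its nominal level; the documents do not support that.

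A reader might also take the 25-29% as the trial's error rate. It is not, because no joint test over visits appears in section 10. The figure shows what would happen if an analyst added one with the default reference, and its main cause is the chi-square reference, not short standard errors.

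The plan does not say that the uncorrected robust variance will be used. A model-based standard error with the correct working correlation held 4.7-5.9% in every simulated scenario. So the problem depends on implementation, and the text leaves that choice open.

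The toxicity counts are assumptions too. Dysphonia carries no grade limit and may be common, in which case the shortfall is small (92% coverage with 10 affected). The stated aim is an estimate, not a test. That softens the point without removing it, since an estimate is read with its interval.

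Finally, the correction does not fully repair the sparsest case: with 3 patients affected, coverage rises only to about 91%.

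**Conclusion.** The point holds as a cheap improvement to secondary analyses. If ordinary robust GEE inference is used at a two-sided 5% level, single-visit changes run at about 7% (6.7% at n = 25, 6.9% at n = 22). Intervals for the utility decrement cover about 82% to 92% as the number affected goes from 3 to 10 of 25. Any joint test would run at about 25-29% for PROs and 20% for utilities.

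The patient number, visit counts and recurrence exclusion come from the plan. The variance estimator, reference distribution, test level, correlation and toxicity counts are assumed. The utility decrement matters most, because the plan explicitly promises that coefficient and ordinary GEE would give it intervals that are too narrow. No decision rule rests on these endpoints, and the primary local-failure analysis is unaffected.

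**What to change.** In 10.3.2 and 10.3.2.5, keep GEE and add:
- a Mancl-DeRouen corrected covariance with a t reference for single contrasts and coefficients;
- an F (Hotelling-type) reference, with denominator degrees of freedom based on the number of patients, for any joint test over visits;
- a statement of the working correlation and of the level used for these tests;
- a rule that a toxicity coefficient resting on only about 3 patients is reported as descriptive.

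A mixed model with Kenward-Roger degrees of freedom is an acceptable alternative.

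The cost is a few lines of analysis text and a software option. The downside is slightly wider intervals.
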